4.2 Primary endpoint

- Rate of discontinuation of P2Y12 inhibitors and/or aspirin (without bridging) in the first 3 months after PCI with low risk characteristics and 6 months after PCI with high risk characteristics or any antiplatelet therapy discontinuation without bridging therapy

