4.3 Secondary endpoints

Patients undergoing non cardiac surgery:

- The composite of death, myocardial infarction, probable/definite stent thrombosis according the Academic Research Consortium definition⁴⁴ and bleeding events of Bleeding Academic Research Consortium (BARC) grade ≥ 3 at 30 days
- The composite of death, myocardial infarction and probable/definite stent at 30 days
- The incidence of bleeding events of Bleeding Academic Research Consortium (BARC) grade ≥ 3 at 30 days
- The type and the length of discontinuation of any antiplatelet therapy in patients undergoing non cardiac surgery according to time from PCI to surgery
- Rate of non cardiac surgical procedures within 12 months from PCI divided into quartiles (0-3, 3-6, 6-9, 9-12 months)
- Delay in performing non cardiac surgical procedure

Patients undergoing cardiac surgery:

- The composite of death, myocardial infarction, probable/definite stent thrombosis according the Academic Research Consortium definition⁴⁴ and bleeding events of Bleeding Academic Research Consortium (BARC) grade ≥ 4 at 30 days
- The composite of death, myocardial infarction and probable/definite stent at 30 days
- The incidence of bleeding events of Bleeding Academic Research Consortium (BARC) grade ≥ 4 at 30 days
- The type and the length of discontinuation of any antiplatelet therapy in patients undergoing cardiac surgery according to time from PCI to surgery
- Rate of cardiac surgical procedures within 12 months from PCI divided into quartiles (0-3, 3-6, 6-9, 9-12 months)
- Delay in performing cardiac surgical procedure

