4.5.4 Follow-up

A follow-up contact visit is planned at 30 days (\pm 7 days) after the surgical procedure using hospital records, outpatient visits, or telephone contact. A standard questionnaire will be used to collect information on the medications the patients were taking and the occurrence of any adverse events. Each site will have a designated individual who entered raw data into an electronic case report form, allowing immediate and continuous monitoring of its completeness and accuracy. Unscheduled visits can also take place whenever necessary.

Relevant information to be inquired and collected in the e-CRF will include:

- check of items describing the primary and secondary study endpoints, with special reference to new hospitalizations;
- ongoing medications
- compliance with medication prescribed at discharge
- adverse events

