7.2 Description of Statistical Methods

Continuous numeric variables will report as means with SD and compared using the Student’s t- or Wilcoxon rank-sum test. Categorical variables will be presented as counts and percentages and will be compared using the chi-square or Fisher’s exact test. To examine the effect of significant factors on two different groups (Group 1 vs Group 2) the hazard ratio of the interaction term will be calculated. To identify the independent predictors for in hospital NACE, 30day MACE and 30-day BARC bleedings, first univariate and then multivariate logistic regression models will apply. The BARC bleedings will be considered according to type of surgery. Specifically, BARC bleedings grade ≥ 3 will be considered in patients undergoing cardiac surgery, and BARC bleedings grade ≥ 4 will be taken into account for non-cardiac surgery. Covariates for multivariable models will be selected on the basis of a backward stepwise algorithm in a Cox proportional hazards model. Additionally, to minimise group differences on confounding covariates between patients who will be managed with consensus document (group 1) and those who will be received local practice (group 2), a 1:2 propensity score matching would be used. Propensity scores will be calculated with logistic regression, with multiple imputation and backwards elimination with a significance level to stay of 0.05. To ensure that the comparison between two groups (group 1 vs group 2) would not be bias, the proportion of patients who will not received consensus document within center that traditionally used it, will be excluded. The results will be presented as ORs with 95% confidence intervals (CI) and p values. For all

analyses, a two-sided $P <0.05$ will be required for statistical significance. All data will be analyzed using the Statistical Package of Social Sciences version 20 (IBM SPSS, Chicago, IL).

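### Section 7.2 reports odds ratios from logistic models but selects their covariates in a Cox model and gives effect modification as a hazard ratio

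*Combined protocol and SAP*

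**What the plan says.** All four relevant statements stand in one paragraph of the combined protocol and SAP, Section 7.2.

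- Outcomes: the aim is "To identify the independent predictors for in hospital NACE, 30day MACE and 30-day BARC bleedings".
- Model for those outcomes: "first univariate and then multivariate logistic regression models will apply".
- Covariate selection: "Covariates for multivariable models will be selected on the basis of a backward stepwise algorithm in a Cox proportional hazards model".
- Effect modification between Group 1 (SAS 2 document) and Group 2 (local practice): "the hazard ratio of the interaction term will be calculated". No outcome or model is named for this step.
- Reporting scale: "The results will be presented as ORs with 95% confidence intervals (CI) and p values".

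Section 4.3 defines the clinical endpoints as composites or incidences at a fixed point, for example "The incidence of bleeding events of Bleeding Academic Research Consortium (BARC) grade ≥ 3 at 30 days" in non-cardiac surgery. Section 4.5.4 provides one scheduled contact after surgery: "A follow-up contact visit is planned at 30 days", with a window of 7 days either side.

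**The concern.** The only multivariable outcome models that Section 7.2 names are logistic. The Cox model thus appears only as a device for choosing covariates for a different model, and the hazard ratio for the interaction has no stated parent model.

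To run the Cox step, an analyst would have to decide what counts as the event time, when a patient is censored and, for in-hospital NACE, how discharge alive is treated. The plan settles none of these. It also gives no level to stay for this step; the 0.05 level in Section 7.2 belongs to the propensity model.

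Two statisticians following the text could therefore arrive at different covariate sets and different interaction estimates. The comparison is not randomised, so covariate adjustment carries real weight. A reader would also be given a main result on the odds scale and an interaction on the hazard scale, which cannot be combined.

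**Working it through.** The plan states no figure for this point, so there is none to reproduce. The check has two parts: a comparison of the text, and an illustration of how far the two scales differ. The documents give no event rates, so every risk below is an assumption.

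**1. Does the plan define a time-to-event analysis for the three modelled outcomes?**

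| Element needed for a Cox model | What the plan gives |
|---|---|
| Event indicator | Yes: in-hospital or 30-day event |
| Time origin | Implied only: follow-up is counted from surgery (4.5.4) |
| Event time as part of the endpoint | Not defined; endpoints are status at 30 days (4.3) |
| Censoring rule | None |
| Handling of discharge for in-hospital NACE | None |
| Cox outcome analysis, Kaplan-Meier, log-rank or proportional-hazards check | None |
| Reporting scale | Odds ratio (7.2) |

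The Cox step and the hazard ratio therefore have no defined analysis behind them.

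**2. How far apart are the two scales over a fixed window?**

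Formulas, assuming proportional hazards and complete follow-up:

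- OR = [p1/(1−p1)] / [p0/(1−p0)]
- HR = ln(1−p1) / ln(1−p0)

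Uncommon event, assumed 5% vs 8%:

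- OR = (0.08/0.92)/(0.05/0.95) = 0.0870/0.0526 = 1.65
- HR = ln(0.92)/ln(0.95) = 0.0834/0.0513 = 1.63

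Common event, assumed 30% vs 45%:

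- OR = (0.45/0.55)/(0.30/0.70) = 0.8182/0.4286 = 1.91
- HR = ln(0.55)/ln(0.70) = 0.5978/0.3567 = 1.68

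**3. What does this do to an interaction?**

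Suppose a factor has HR 2.0 in both groups, so that the interaction HR is exactly 1. Then p1 = 1−(1−p0)², and the implied odds ratios are:

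| Assumed baseline risk p0 | p1 | OR |
|---|---|---|
| 2% | 3.96% | 2.020 |
| 5% | 9.75% | 2.053 |
| 10% | 19% | 2.111 |
| 30% | 51% | 2.429 |
| 50% | 75% | 3.000 |

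The ratio of odds ratios between two groups with different baseline risks is then:

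- 2% vs 10%: 2.111/2.020 = 1.045
- 5% vs 30%: 2.429/2.053 = 1.183
- 10% vs 50%: 3.000/2.111 = 1.421

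No interaction on the hazard scale can thus appear as an interaction on the odds scale. The discrepancy is slight when events are uncommon in both groups and clear when they are common in one. These figures compare effect scales. They do not measure how often the Cox step would choose different covariates.

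**The case against.** The strongest reply is that little would change in practice. With uncommon events and nearly complete follow-up to 30 days, Cox and logistic regression give similar estimates and will often keep the same covariates. A small simulation under assumed conditions points the same way. It used 1,623 patients, ten independent normal covariates, true proportional hazards, complete 30-day follow-up, backward elimination at 0.05 and 40 runs. The two methods kept the identical set in about 93% of runs at about 5% events and about 83% at about 36% events. With so few runs, and conditions that favour agreement, this is illustration only. The point stands, however, and it limits the claim about size.

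Three stronger readings are tempting, and the documents do not support them.

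- *That the primary endpoint is being given a hazard it does not have.* Section 7.2 assigns no regression model to the primary endpoint. Section 4.5.3 also records dates and times of discontinuation and reinstitution, so timing data will exist.
- *That the plan contains no endpoint measured in time.* Section 4.3 lists length of discontinuation and delay to surgery, and Section 6.6 gives the delay a start and an end. Because the interaction sentence names no outcome, one could argue that its hazard ratio was meant for these. But no regression is assigned to them either, and the results are to be given as odds ratios.
- *That covariates chosen in a Cox model make the adjusted odds ratios materially wrong.* Nothing in the documents shows this, and the odds ratio and hazard ratio pairs above cannot show it.

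None of this explains why the covariates of a logistic model should be chosen in a Cox model, or what the interaction hazard ratio is estimated from.

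**Conclusion.** The point holds as an inconsistency in a stated analysis, and it should be corrected. For in-hospital NACE, 30-day MACE and 30-day BARC bleeding, the covariate selection and the interaction measure come from a model that the plan neither defines nor reports. As written, those analyses cannot be reproduced, and the interaction hazard ratio cannot be set beside the odds ratios.

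The expected numerical effect is small for uncommon 30-day events (1.65 against 1.63 at 5% vs 8%) and grows with event frequency (1.91 against 1.68 at 30% vs 45%). These sizes rest on assumed risks, proportional hazards and complete follow-up. Incomplete follow-up or non-proportional hazards could widen the gap. The conclusion about coherence rests on the text alone and needs none of these assumptions.

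The finding is confined to the predictor and interaction analyses. It does not extend to the primary endpoint comparison.

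**What to change.** In Section 7.2:

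1. Delete the Cox selection step, and select covariates within the same logistic model that is fitted and reported for each outcome. State the level to stay for that selection.
2. Delete the hazard ratio. Test each group-by-factor interaction in that logistic model, name the outcomes and factors concerned, and report the ratio of odds ratios with its 95% CI.

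If the sponsor does want hazard ratios, the coherent alternative is to define event time, origin and censoring for each outcome and to report hazard ratios throughout. That is a larger change.

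A prespecified covariate list in place of univariate screening and stepwise selection is optional. It is a separate choice that would need clinical input, and it is not needed to cure this mismatch.

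The cost of steps 1 and 2 is a few sentences in Section 7.2, with no new data and no change to the eCRF. The wording should be settled before any outcome data are analysed, and so before the first interim analysis at 800 patients (Section 7.1).

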4. STUDY DESIGN

4.1 Summary of Study Design

The SAS registry will include any patient with previous coronary stenting undergoing any type of surgery or operative endoscopic/endovascular procedure at the participating Centers. Centers will be divided into two groups: Centers that routinely follow the recommendations of the SAS 2 Document and Centers that do not. The relevant clinical, procedural and outcome data (within index admission and at 30 days) will be entered in a specifically designed electronic case record form (eCRF).

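### Secondary endpoints are defined separately for cardiac and non-cardiac surgery, but the propensity match is not tied to surgery type, so balance within each stratum is not assured

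*Combined protocol and SAP*

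**What the plan says.** Section 4.1 enrols "any patient with previous coronary stenting undergoing any type of surgery or operative endoscopic/endovascular procedure at the participating Centers", so both kinds of surgery enter one registry. Section 4.3 then gives two parallel lists of six secondary endpoints, one headed "Patients undergoing non cardiac surgery" and the other "Patients undergoing cardiac surgery", with a different BARC threshold in each. No secondary endpoint is pooled over the two. The primary endpoint in section 4.2 is not split by surgery type.

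Section 7.2 plans to reduce confounding between group 1 (consensus document) and group 2 (local practice): "a 1:2 propensity score matching would be used". On the score it says: "Propensity scores will be calculated with logistic regression, with multiple imputation and backwards elimination with a significance level to stay of 0.05". It gives no covariate list, exact-match factor, caliper or balance check, and it does not say which endpoints are analysed in the matched sample. Surgery type appears in that section only for the bleeding endpoint: "The BARC bleedings will be considered according to type of surgery".

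**The concern.** A propensity score balances covariates in the population for which it is estimated and matched. If that population is all patients together, balance holds on average over cardiac and non-cardiac surgery. It need not hold inside either one, and that is where every secondary endpoint sits.

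Two features of section 7.2 add to the risk. Backward elimination at 0.05 keeps a covariate only if it predicts group membership, so surgery type can drop out. No interaction of type with other covariates is foreseen.

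The groups also come largely from different centers (section 4.1). Differences in case mix are then center differences, which may not be the same for cardiac and non-cardiac patients. That last step is an inference, because the documents give no case mix.

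At stake is whether a matched comparison of, for example, the 30-day composite in cardiac patients is adjusted for confounding at all. An overall balance table would not show the failure.

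**Working it through.** **The plan's own figure.** There is no balance figure to reproduce. The sample size of 1,623 (section 7.1) comes without event rates or an effect size, so it cannot be re-derived; it is used here only as N.

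**Mixed sets, closed form.** If surgery type is ignored and the cardiac share is p, the chance that a set of three contains both types is 1 − p³ − (1 − p)³.
- p = 0.10: 1 − 0.001 − 0.729 = 27%
- p = 0.20: 1 − 0.008 − 0.512 = 48%

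**Simulation inputs.** From the plan: N = 1,623, a logistic score and 1:2 matching, read as one group 1 patient to two group 2 patients. Assumed:
- cardiac share 10% or 20%;
- greedy nearest-neighbour matching without replacement, caliper 0.2 SD of the logit;
- log-odds of group 1 = −1.3 + 0.3 × type + b × confounder + 0.3 × second covariate;
- b = 0.5 in both types (same link), or 0.5 in non-cardiac and −0.3 in cardiac patients (different link);
- 25 runs per scenario.

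The table gives the standardised difference of the confounder in SD. Each pair of values is for a cardiac share of 10% / 20%.

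| Link | Matching | Sets | Mixed sets | Overall, mean | Non-cardiac, mean | Cardiac, mean | Cardiac, mean absolute |
|---|---|---|---|---|---|---|---|
| Same | Pooled, type in score | 352 / 362 | 29% / 47% | −0.00 / 0.01 | −0.00 / −0.00 | −0.00 / 0.04 | 0.11 / 0.09 |
| Same | Within type, separate scores | 343 / 351 | 0% | 0.00 / −0.00 | −0.00 / −0.00 | 0.02 / −0.00 | 0.03 / 0.03 |
| Different | Pooled, type omitted | 351 / 357 | 30% / 52% | 0.00 / 0.00 | 0.08 / 0.15 | −0.62 / −0.54 | 0.62 / 0.54 |
| Different | Pooled, type in score | 357 / 362 | 29% / 50% | 0.00 / −0.00 | 0.08 / 0.16 | −0.58 / −0.56 | 0.58 / 0.56 |
| Different | Pooled, type and interaction | 346 / 359 | 29% / 50% | 0.00 / 0.00 | 0.00 / 0.00 | 0.03 / −0.01 | 0.05 / 0.04 |
| Different | Within type, separate scores | 345 / 350 | 0% | 0.01 / −0.00 | 0.01 / 0.00 | −0.01 / −0.02 | 0.04 / 0.04 |

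**Intermediate case.** If the confounder has no link with group in cardiac patients, the mean absolute cardiac difference was 0.38 to 0.42 SD in a further check at N = 1,623, and 0.28 to 0.33 SD in a separate simulation at N = 2,400. In the further check the same-link case gave 0.11 to 0.14 SD, and matching within type gave 0.03 to 0.14 SD.

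**Loss of sets.** Matching within type against pooled matching with type in the score: (352 − 343)/352 = 2.6%, (362 − 351)/362 = 3.0%, (357 − 345)/357 = 3.4% and (362 − 350)/362 = 3.3%.

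**What drives the imbalance.** With the interaction in the score, 29% to 50% of sets remain mixed, yet both strata are balanced. The cause is a score that is wrong inside the stratum. Mixed sets do not cause it.

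**The case against.** The strongest reply is that nothing here shows harm. Section 7.2 is silent on surgery type; it does not exclude it. In the same-link case the cardiac difference is no larger than chance would leave between randomised groups. With about 40 against 80 cardiac patients (10% share), the expected absolute difference is 0.80 × √(1/40 + 1/80) = 0.15 SD; with 82 against 164 (20% share) it is 0.80 × √(1/82 + 1/164) = 0.11 SD. The simulated 0.11 and 0.09 SD lie below these. Material imbalance needs a link that differs by type, which the documents neither support nor exclude. Section 4.3 lists endpoints without promising a matched contrast for each, and some, such as procedure rates by time from PCI, are naturally descriptive. Section 7.2 also plans multivariable models.

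Much of this stands, and it rules out four stronger readings that a reader might infer:

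- *That the plan states a single match over all patients.* This is the natural reading, but the text does not say it.
- *That balance is lost within the strata.* With the same link there is no systematic loss.
- *That sets mixing the two types are themselves a bias.* Matching on a score balances distributions; set members need not agree on each covariate. Section 7.2 names no analysis that conditions on the set.
- *That the primary endpoint is affected.* It is not split by type, and overall imbalance was near zero in every scenario.

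What the reply does not answer is that the plan contains nothing to prevent or detect the differing-link case. The overall balance table looks the same in both cases.

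**Conclusion.** The point holds for matched comparisons of the secondary endpoints. These are defined within surgery type, while the match as written is not tied to type, may lose type from the score and has no balance check by stratum. Depending on details the plan leaves open, the average imbalance of a confounder in the cardiac stratum ranges from about 0.1 SD (noise) to about 0.3 to 0.6 SD (systematic), with overall imbalance near zero. The non-cardiac stratum is less exposed: 0.08 to 0.16 SD in the differing-link case.

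These sizes rest on an assumed cardiac share of 10% to 20%, assumed confounder links and an assumed matching algorithm. They show what the plan allows and do not predict what will happen. The correction is cheap and should be made before analysis.

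**What to change.** In section 7.2, state that:

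1. 1:2 matching is exact on surgery type (cardiac or non-cardiac).
2. The propensity score uses a prespecified covariate list and always keeps surgery type. Where numbers allow, it includes interactions of type with key covariates, or a separate score is fitted for each type.
3. Standardised differences are reported within each stratum as well as overall.
4. The secondary endpoints to be compared in the matched sample are named.

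The cost is SAP wording, possibly one more model fit, and up to about 3% of matched sets in simulation. No extra patients or data are needed.

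A separate cardiac score may be unstable. At a 10% share there would be about 0.10 × 1,623 = 162 cardiac patients over both groups, and about 0.10 × (324 + 162) = 49 in the one-year subset of section 7.1. If numbers are that small, use a common score with exact matching on type. Without interactions, that option reduces imbalance from differing links but does not remove it, so the stratum balance table is then essential and any remaining differences should be adjusted for.

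A separate matter affects the same strata: section 7.2 assigns BARC ≥3 to cardiac and ≥4 to non-cardiac surgery, the reverse of section 4.3. The two sections must be reconciled.

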4.5.3 In-hospital assessments

The MONET registry does not imply any assessments additional to routine treatment. The following clinical and laboratory variables will be captured by the eCRF:

Clinical characteristics

- Age, gender, body weight.
- Selected coronary risk factors, such as diabetic status, smoking, hypertension, dyslipidemia.

- Cardiovascular status: prior MI, PCI (date of latest stenting), CABG, heart failure, atrial fibrillation, latest left ventricular ejection fraction.

Laboratory tests

- Baseline serum creatinine (eGFR will be automatically calculated by the eCRF using the Cockcroft-Gault formula) and peak serum creatinine during hospital stay.
- Baseline haemoglobin/haematocrit and nadir values during hospital stay.
- CKMB and troponin values should be checked at 6-hour intervals for 24 hours after any suspect ischemic symptoms and/or ischemic ECG changes in the perioperative period, unless otherwise recommended by local practice. The peak value of CKMB will be recorded in the eCRF.

Electrocardiogram

A standard 12-lead ECG will be taken preoperatively, in the case of ischemic symptoms and at discharge.

Concomitant Medications

The following medications will be captured by the eCRF:

- Aspirin
- P2Y₁₂ inhibitors (further subdivided as ticlopidine, clopidogrel, prasugrel, ticagrelor)
- Betablockers
- Statins
- ACEI, ARBS
- Oral anticoagulants (warfarin, acenocumarol, apixaban, dabigatran, edoxaban, rivaroxaban)

- Low-molecular weight heparin
- Tirofiban or eptifibatide
- Cangrelor

The dates and times of perioperative discontinuation and reinstitution (if any) will also be captured.

Drug therapy at discharge and at the 30-day contact will be captured by the eCRF.

Index PCI and surgical procedure details

Details of PCI and surgical procedures will be obtained from interrogation of the medical records and hospital charts.

The delay from stenting to surgery and the type of stent (BMS, first or second generation DES), stent number, length and diameter will be recorded. Surgeries will risk-stratified according to the American College of Cardiology/American Heart Association classification [11]. Moreover, the American Society of Anaesthesiologists (ASA) physical status will be assessed for each patient [21].

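### Backward elimination at 0.05 selects propensity-score covariates on their link to group alone, so prognostic covariates with small group differences are often dropped and may stay unbalanced after matching

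*Combined protocol and SAP*

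**What the plan says.** The comparison is not randomised. Section 4.1 divides sites into "Centers that routinely follow the recommendations of the SAS 2 Document and Centers that do not". To reduce confounding between the two groups, Section 7.2 states that "a 1:2 propensity score matching would be used". It continues: "Propensity scores will be calculated with logistic regression, with multiple imputation", and then "backwards elimination with a significance level to stay of 0.05".

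Neither Section 7.2 nor any other section lists candidate covariates, forces any into the score, sets a caliper, requires a balance check after matching, or says what to do about covariates left unbalanced.

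Section 7.2 also plans multivariable models. Their purpose is "To identify the independent predictors for in hospital NACE, 30day MACE and 30-day BARC bleedings", and "Covariates for multivariable models will be selected on the basis of a backward stepwise algorithm in a Cox proportional hazards model". The primary endpoint in Section 4.2, antiplatelet discontinuation, is not among those outcomes.

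Section 4.5.3 lists the recorded variables, for example "Selected coronary risk factors, such as diabetic status, smoking, hypertension, dyslipidemia". It also lists cardiac history, ejection fraction, creatinine, haemoglobin, drugs, stent details and ASA status, and says that the SAS 2 bleeding and thrombotic risk classes will be assigned at analysis. Nothing links these variables to the score.

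**The concern.** A confounder must be related to both group and outcome. The stay rule tests only the first relation, and it tests significance rather than size. A strong predictor of discontinuation or of events that differs modestly between groups can fail at 0.05 and leave the score. Matching then has no reason to balance it, except through its correlation with covariates that were kept. This works against the purpose that Section 7.2 gives for the matching.

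What is at stake is residual confounding in the group 1 versus group 2 odds ratio. It matters most for the primary endpoint, for which the plan names no other covariate adjustment. Section 7.2 also excludes patients at SAS 2 centres who were not managed by the document, but that is a restriction and balances nothing.

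**Working it through.** **Inputs from the documents.** Section 7.1: 1,623 patients in total, and a subset of 324 versus 162 within one year of stenting. Section 7.2: two-sided 0.05, 1:2 matching, stay level 0.05. The total of 1,623 cannot be reproduced, because no event rates are given: at 1:2, 80% power and two-sided 5%, both 16% versus 11% and 30% versus 37% give 1,614. It serves here only as the sample size.

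**Assumptions.** Group split, event rate, covariate effects and caliper are not in the documents.

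**Step 1: how large a difference can be dropped.** For a standardised difference d and group sizes a and b, SE = √(1/a + 1/b). A covariate fails the stay rule if its observed difference is below 1.96 × SE (univariate approximation). The chance of being dropped is 1 − [Φ(d/SE − 1.96) + Φ(−d/SE − 1.96)].

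Example with 541:1082: SE = √(1/541 + 1/1082) = 0.0527, so the limit is 1.96 × 0.0527 = 0.103. For d = 0.10, d/SE = 1.90 and the chance of being dropped is 52%.

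| Split | Largest observed d that can be dropped | d = 0.05 | 0.10 | 0.15 | 0.20 |
|---|---|---|---|---|---|
| 811:812 | 0.097 | 83% | 48% | 14% | 2% |
| 541:1082 | 0.103 | 84% | 52% | 19% | 3% |
| 325:1298 | 0.122 | 87% | 64% | 32% | 10% |
| 324:162 | 0.189 | 92% | 82% | 66% | 45% |

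SE is symmetric in a and b, so the last row holds whichever group is the larger.

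**Step 2: bias from one dropped confounder.** Approximately (outcome OR per SD)^d. At d = 0.10 this is 1.5^0.10 = 1.04, 2^0.10 = 1.07 and 3^0.10 = 1.12. One such omission is modest.

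**Step 3: several confounders, weak group links.** Simulations with no true effect, N = 1,623, about 25% in group 1, independent covariates, 1:2 caliper matching and assumed event rates (15% or about 20% where noted). There were 200 to 520 replicates per run; ranges cover repeated runs. Each cell gives elimination versus all covariates kept.

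| Scenario (ORs per SD) | Dropped | Spurious difference, points | False positives |
|---|---|---|---|
| 10 confounders, group OR 1.1, outcome OR 1.35, all aligned | 5.9–6.1 | 1.7–2.0 vs 0.1 | 9.0–10.7% vs 1.9–3.7% |
| 6 confounders, group OR 1.1, outcome OR 1.5, all aligned | 3.5–3.8 | 1.5–1.6 vs 0.2 | 7.5–9.3% vs 3.0–3.1% |
| 10 confounders, random directions | 6.2 | 0.3 vs 0.2 | 3.4% vs 3.0% |
| 6 confounders, random directions | – | – | 4.4% vs 3.0% |
| Group OR 1.3, all aligned | 0.07 | – | 3.8% vs 4.4% |

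With directions alternating, mean bias under elimination was 0.0 points and false positives 5.0%. The imbalance itself does not depend on direction. With 10 confounders, at least one kept a standardised difference above 0.1 in 66–72% of replicates, aligned or not, against 0% with all kept.

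**Step 4: a second set-up.** Four confounders, d = 0.05 to 0.15, outcome OR 2 per SD, event rate 15%, 300 replicates per scenario.
- N = 1,623 (325 or 438 in group 1): the null OR drifts to 1.04–1.11 with elimination, against 1.00–1.02 with the full score. False positives are 3.7–8.7% against 1.3–6.3%.
- N = 324 + 162 = 486 (97 in group 1): the null OR drifts to 1.09–1.21, against 0.99–1.00. Even the full score leaves a difference above 0.1 in 27–31% of replicates, against 89–91% with elimination.

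**The case against.** The strongest reply is that the harm is conditional and bounded. At full size a dropped covariate has an observed difference of at most about 0.12, close to the usual 0.1 limit for acceptable balance. When imbalances point in mixed directions, their effects largely cancel. When group links are stronger (OR 1.3 per SD), almost nothing is dropped. Dropped covariates that correlate with retained ones would be partly balanced, and the simulations ignored this. The false-positive contrast is also helped by a conservative comparator, since the full-score rates are mostly below 5%. Monte Carlo error matters too: 7.5% from 520 replicates has a 95% interval of 7.5 ± 1.96 × √(7.5 × 92.5/520), about 5.2 to 9.8%. All of this stands, and it limits the size of the claim. It does not justify the rule, because the sponsor cannot know beforehand that the imbalances will cancel.

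A reader might infer that matching is the plan's only defence against confounding. That goes too far. Section 7.2 adds multivariable models for NACE, MACE and BARC bleeding, which select on association with outcome. They are framed as searches for predictors, and the text does not say that group is a term in them, but they exist. The narrower statement holds for the primary endpoint.

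A reader might also infer that every variable recorded before surgery belongs in the score. Time from PCI does not clearly belong. Section 2 shows that SAS 2 guidance bears on when to operate after PCI, so the strategy may affect it, and its distribution is a secondary endpoint (Sections 4.3 and 6.5). Nor can one say that every candidate is already in the eCRF: urgency appears in the eligibility text (Section 4.4.1) but is not itemised in Section 4.5.3.

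**Conclusion.** The concern holds in this form. The written rule keeps covariates for their association with group alone, and nothing else in the plan forces prognostic covariates in or checks balance. A covariate with a true standardised difference of 0.10 is dropped with probability 48–64% at N = 1,623 and 82% in the 324 versus 162 subset.

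The consequence for the estimate depends on inputs that the documents do not give. It runs from about 0 to about 1.5–2 percentage points of bias, with false positives of about 7–10% at the upper end (7.5–10.7% across runs). The upper end requires many weak imbalances that all favour the same group. That is plausible if centres differ in overall case mix, but the documents do not show it. They therefore do not support the stronger inference that the primary comparison will be biased or that its false-positive rate is inflated in general. The change should be made because it is cheap and the direction of the imbalances cannot be known in advance.

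**What to change.** In Section 7.2, delete the backward elimination from the propensity model and replace it with the following:

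- A prespecified covariate list, retained regardless of p-value and drawn from pre-exposure variables in Section 4.5.3: demographics, coronary risk factors, cardiovascular history, ejection fraction, baseline creatinine/eGFR and baseline haemoglobin (not peak or nadir values), stent details, baseline antithrombotic drugs, ASA status, and SAS 2 surgical bleeding and thrombotic risk class. Add urgency if the sponsor confirms that it is recorded.
- Standardised differences reported after matching, with adjustment in the outcome model for any covariate above 0.1. This is needed especially in the within-one-year subset, where even the full score can leave such differences.
- Time from PCI, and any risk-class component derived from it, not used for matching when timing-of-surgery endpoints are analysed. For other endpoints, time from PCI enters only in a stated sensitivity analysis.

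The cost is a wording change, plus a check that urgency is captured. A few more patients may go unmatched: about 2 to 4 of 400 matched sets in simulation, or 0.5 to 1%.
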